PROTOCOL OF A THESIS FOR PARTIAL FULFILMENT OF MASTER DEGREE IN ENDOCRINOLOGY

Title of the Protocol: The impact of Mediterranean Diet on patients with Hashimoto Thyroiditis

FMASU MS 232/2023

4/4/2023

**Faculty of Medicine
Ain Shams University
2023**

What is already known on this subject? And what does this study add?

Hashimoto's thyroiditis (HT) is an autoimmune disease affecting the thyroid gland, and is one of the most common causes of hypothyroidism. Eating habits may affect the risk of several inflammatory and immune diseases as HT. The current knowledge of the diet in HT is insufficient (**Mikulska et al., 2022**). The Mediterranean diet (MD) is an anti-inflammatory diet characterized by frequent consumption of olive oil, unrefined cereals, fresh or dried fruit and vegetables, moderate amounts of fish, dairy and meat, and many condiments and spices. It is rich in nutrients and bio actives which have the potential to offer anti-inflammatory aspect (**Forsyth et al., 2018**). This study aims to assess MD as a dietary intervention in HT patients.

1. INTRODUCTION/ REVIEW

Hashimoto's thyroiditis (HT) is the most frequent autoimmune thyroid disorder. It is the leading cause of hypothyroidism in the iodine-sufficient areas of the world. Pathogenesis of the disease is thought to be a combination of genetic susceptibility and environmental factors that lead to the loss of immunological tolerance, with a consequent autoimmune attack to the thyroid tissue and appearance of the disease(**Ragusa et al., 2019**). There is growing evidence of the existence of a thyroid–gut axis that controls many autoimmune disorders, and patients frequently report changes in their quality of life and thyroid function as a result of dietary modifications (**Danailova et al., 2022**).

The pathologic features of lymphocytic infiltration, especially of T cells, and follicular destruction are the histological hallmark of autoimmune thyroiditis (AIT), that lead to gradual atrophy and fibrosis. An important role in the immune-pathogenesis ofAITDs is due to inflammatory chemokines and cytokines (**Ragusa et al., 2019**). HT is associated with various thyroid functional states ranging from euthyroid, subclinical to overt hypothyroidism. The most common lab findings demonstrate elevated thyroid-stimulating hormone (TSH) and low

thyroxine (T4) levels, coupled with increased antithyroid peroxidase (anti-TPO) antibodies (**Caturegli et al., 2014**).

Weight gain is frequently the first symptom of hypothyroidism. Research has shown that even when HT patients achieve an euthyroid state, 82% of women treated still have excess body weight, and 35% of them suffer from obesity (**Danailova et al., 2022**). Additionally, euthyroid individuals with HT continue to suffer from symptoms, such as chronic fatigue, dry skin, hair loss, chronic irritability, and nervousness, impairing quality of life (**Ott et al., 2011**).

There is mounting evidence for the existence of a robust thyroid–gut axis. It is reflected by a significant influence of the intrinsic bacterial microflora in the gut on the immune system reactivity and the thyroid function. Dysbiosis may significantly impair the immune system and compromise inflammatory control, causing autoimmune illnesses such as autoimmune thyroid diseases (**Knezevic et al., 2020**). Dysbiosis can also directly affect thyroid hormone levels due to bacterial deiodinase activity and TSH inhibition (**Golan et al., 2013**).

The premise behind an anti-inflammatory diet as MD is that oxidative stress may be a significant risk factor in the pathogenesis and progression of HT and the development of complications. Therefore, appropriate lifestyle changes should be implemented, including diet and body weight normalization to reduce oxidative stress in these patients. Some vitamins, such as vitamin A, E, or C, and minerals, including Se, which are found in fresh and raw foods, exhibit antioxidant properties. Frequent consumption of these foods reinforces antioxidant defense mechanisms (**Bjørklund & Chirumbolo, 2017**).

For most HT patients, the hormone-replacement therapy with levothyroxine is indispensable. Nevertheless, an appropriate dietary regimen and ecological lifestyle can complement the standard treatment and favor remission of HT by improving the function of the thyroid gland, as well as by regulating the levels of TSH, T3, T4, anti-TPO antibodies. There is still no specific diet recommended for patients with HT, but an anti-inflammatory diet may help HT patients to reduce the need for medicines, slow down the course of the disease, and avoid relapses (**Ihnatowicz et al., 2020**).

Mediterranean diet (MD) is one of the most common anti-inflammatory diets. It is characterized by a large consumption of fruit, vegetables, legumes, nuts, fish, complex carbohydrates, and extra virgin olive oil (EVOO), and a low intake of processed meats, red meats, and sweets. The MD pattern provides a small amount of saturated fatty acid and a high quantity of antioxidants and fiber derived from fruits, vegetables, and EVOO (**Bellastella et al., 2022**). It is conceivable that adoption of this dietary pattern could be protective against HT, counteracting the deleterious effects of oxidative stress and exerting anti-inflammatory and immunomodulatory actions, most likely by affecting cytokine production and gut microbiota composition (**Ruggeri et al., 2021**).

Goitrogens refer to a group of micronutrients that can cause enlargement of the thyroid gland. It includes two main categories which are cruciferous vegetables and soy products. Goitrogens have been shown to inhibit thyroid hormones synthesis in several ways, mostly by inhibiting iodine utilization. Those micronutrients have to be taken in consideration specially in those with thyroid diseases or who are iodine deficient (**Babiker et al., 2020**).

2. AIM/ OBJECTIVES

This study aims to assess the impact of Mediterranean diet on patients with Hashimoto thyroiditis using the following outcomes:

Primary outcomes: Anti-TPO antibodies, Anti-Thyroglobulin antibodies, TSH, T3, T4

Secondary outcomes: BMI, Lipid profile, Symptoms of hypothyroidism

3. METHODOLOGY:

Patients and Methods/ Subjects and Methods/ Material and Methods

- All participants will be subjected to an interview questionnaire including data pertaining name, age, sex, occupation, past medical history, 24 hours dietary recall, general clinical examination, anthropometric measures of weight, height, BMI, and biochemical Investigations including Lipid profile (Cholesterol/HDL ratio, triglycerides), HbA1C, TSH, free T3, free T4, Anti-TPO, Anti-Thyroglobulin.
- **Type of Study:** single-arm open label clinical trial
- **Study Setting:** Outpatient clinics of Ain Shams University hospitals, Cairo, Egypt.
- **Study Population:** this study will be conducted on patients with HT
- **Inclusion Criteria:**
 1. - Female and male patients with HT diagnosed by a combination of clinical features of hypothyroidism and presence of anti-thyroid antibodies.
 2. - Age from 20 to 50 years old
- **Exclusion Criteria:**
 1. -Pregnant or lactating females
 2. -Age below 20 years and above 50 years
 3. -presence of any other medical disorder
- **Pre-intervention Baseline assessment:**
 1. Anti-TPO
 2. Anti-Thyroglobulin
 3. TSH, free T3, free T4
 4. BMI (measured in kg/m²)
 5. Lipid profile (Total Cholesterol, HDL, LDL, Triglycerides)
 6. HBA1C, Fasting Blood Sugar, 2 hours Post Prandial

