8. ESR

- **Sample Size:** Using the G power program for sample size calculation, setting power at 80% alpha error at 5%, reviewing results from previous studies (Danailova et al, 2022, and Bellastella et al, 2022) showed that HT patients showed a high intake of animal proteins, saturated fats, and refined sugar-in other words, the prototype of the so-called Western-type diet, in contrast with the Mediterranean one. Also, intake of the Mediterranean diet is associated with improving symptoms, assuming an effect size difference =0.5 regarding AB levels before and after dietary intervention and after a 10% adjustment for dropout rate, a sample size of at least 40 patients will be needed.
- **Sampling Method:** Convenience sampling such as that all male and female patients with HT will be invited to join the Mediterranean Diet regimen. Those who agree to participate and provide a written informed consent will be enrolled in the study.
- **Adverse events:** Possible adverse events in terms of anemia or disturbance of lipid profile will be assessed at 3 months and the patient withdrawn from the study if they occur.
- **Ethical Considerations:** A written informed consent will be obtained from each patient before enrolment in this study.

Statistical Analysis: Data will be collected and entered into the software and edited for errors. Data were expressed as median and interquartile range. Analytical statistics were done using the Wilcoxon rank test and Spearman correlation test. The Wilcoxon rank test was used to compare parameters expressed in median and IQR pre- and post-intervention. The Spearman

correlation test was used to measure the direction and strength of association between different study parameters. The P-value was used to measure the level of significance, where $P > 0.05$: non-significant (NS), $P < 0.05$: significant (S), and $P < 0.01$: highly significant (HS).

- **software to be used:** SPSS (Statistical Package for Social Sciences) version 20 will be the statistics software to be used. Citation of SPSS: IBM Corp. Released 2011. IBM SPSS Statistics for Windows, Version 20.0. Armonk, NY: IBM Corp.

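### Five unranked primary outcomes, each tested at P<0.05 with no success rule, while the sample size of 40 fits a single antibody test

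*Combined protocol and SAP*

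**What the plan says.** Section 2 (Aim/Objectives) gives two lines: "Primary outcomes: Anti-TPO antibodies, Anti-Thyroglobulin antibodies, TSH, T3, T4" and "Secondary outcomes: BMI, Lipid profile, Symptoms of hypothyroidism". Neither is ordered, and no lead outcome is named.

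The Sample Size paragraph of section 3 (Methodology) works from one set of inputs, "setting power at 80% alpha error at 5" per cent, "assuming an effect size difference =0.5 regarding AB levels before and after dietary intervention", and concludes: "after a 10% adjustment for dropout rate, a sample size of at least 40 patients will be needed". It does not say which of the two antibodies is meant, whether the test is one- or two-sided, or which test was chosen in the software. TSH, T3 and T4 have no sizing.

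The Statistical Analysis paragraph says: "The Wilcoxon rank test was used to compare parameters expressed in median and IQR pre- and post-intervention". It labels P<0.05 significant and P<0.01 highly significant, whichever parameter is tested. The outcome list in section 3 merges primary, secondary and undesignated measures and sets no priority. The documents contain no multiplicity adjustment, testing hierarchy or success rule.

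**The concern.** The plan does not say what a positive trial is, and two natural readings each break one of its design figures. If any one significant primary outcome is enough, the 5% error used for the sample size does not describe the primary conclusion. If all five are required, the 80% power does not.

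The practical risk is that one P<0.05 among five is reported as the diet's primary effect, with the choice made after the results are known. The 0.01 label is no safeguard, because P<0.05 already earns the word significant.

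**Working it through.** **Inputs from the documents.** Five primary outcomes (section 2). Alpha 0.05, power 0.80, standardised before/after difference 0.5 for antibody levels, 10% dropout, N = 40 (Sample Size). Wilcoxon test and a 0.05 threshold for each parameter (Statistical Analysis).

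**Assumptions.** The documents give no correlation among the outcomes, so I use a common value from 0 to 0.9. They give no effect for the hormones, so I use 0.5 and, as a less favourable case, 0.3.

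**Step 1: reproduce N = 40.** For a paired t-test, power = P(|T| > t(1−α/2, n−1)), where T is noncentral t with noncentrality 0.5√n. As a first approximation, n = ((1.960 + 0.842)/0.5)² = 31.4; the exact calculation gives 34. For the Wilcoxon test, n is scaled by its relative efficiency for normal data, 3/π = 0.955. Enrolment is n/0.9, rounded up.

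| Test level | Pairs (t / Wilcoxon) | Enrolled |
|---|---|---|
| two-sided 0.05 | 34 / 35 | 38 / 39 |
| two-sided 0.025 (two outcomes) | 41 / 43 | 46 / 48 |
| two-sided 0.01 (five outcomes) | 51 / 53 | 57 / 59 |
| one-sided 0.05 | 27 / 28 | 30 / 32 |

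The stated 40 is within two patients of one two-sided 5% test and further from every other row. With the minimum efficiency of 0.864, the two-sided 0.05 test needs 39 pairs and 44 enrolled, so 40 would fall slightly short even for one test. Forty less 10% leaves 36 evaluable, with single-test Wilcoxon power of 81%.

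**Step 2: any one counts, nothing changes.** If independent, 1 − 0.95⁵ = 0.226 for five outcomes and 1 − 0.95² = 0.0975 for the two antibodies. The Bonferroni ceiling for five is 5 × 0.05 = 0.25. For correlated outcomes I used exact signed-rank tests on 36 simulated pairs with normal differences (20,000 to 40,000 runs); the antibody row is from the normal approximation.

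| Correlation | 0 | 0.3 | 0.5 | 0.7 | 0.9 |
|---|---|---|---|---|---|
| Any of five | 0.221 | 0.209 | 0.187 | 0.154 | 0.105 |
| Either antibody | 0.098 | 0.095 | 0.091 | 0.084 | 0.070 |

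Against 0.05, the five-outcome error runs from 0.226/0.05 = 4.5 times down to about twice.

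**Step 3: all five must be significant.** Power with 36 pairs, same simulation:

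| Correlation | 0 | 0.3 | 0.5 | 0.7 | 0.9 |
|---|---|---|---|---|---|
| All effects 0.5 | 0.36 | 0.46 | 0.52 | 0.60 | 0.69 |
| Hormones 0.3 | 0.04 | 0.11 | 0.15 | 0.21 | 0.29 |

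No entry reaches 0.80.

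**The case against.** The strongest reply is that the plan never promises a family-wise 5%. It uses 5% once, to size an antibody comparison, and otherwise attaches labels to P-values. Reporting five results with unadjusted P-values is defensible in a small, single-arm, open-label thesis study. That would stand if the outcomes were called exploratory. They are called primary, and the trial is sized with an alpha and a power. The inflation is conditional on an any-one reading, and that condition has to be stated with the figure.

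Two further points are fair. First, the 10% end of the range rests on an assumed correlation of 0.9; correlations closer to 1 would bring the rate nearer to 5%. Only the 22.6% figure follows from the independence formula without choosing a positive correlation. Second, N = 40 is closest to one two-sided test but does not match it exactly, and neither the sidedness nor the test is stated.

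It can also be said that the absence of a control group is the larger weakness. That is a separate problem: a multiplicity rule does not correct systematic change over three months. It does not settle which of the five P-values carries the conclusion.

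**Conclusion.** The concern holds, and it should be fixed before analysis. The plan has five primary outcomes, a 0.05 threshold for each, and a sample size that fits one antibody test.

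- **Any one counts:** false-positive chance 22.6% if independent, about 10% at correlation 0.9. If either antibody counts, 9.75% and about 7%.
- **All five required:** no inflation. Power is about 36% to 69% if every effect is 0.5, or 4% to 29% if the hormones have 0.3.

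These figures assume 36 evaluable patients, normally distributed differences and a common correlation. The reproduction of N supports a two-sided test, but the documents do not state one.

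**What to change.** **Preferred.** Before outcome data are seen, the investigator names one antibody at 3 months (anti-TPO, for example) as the single primary outcome, tested at two-sided 5%, and states this in both the objectives and the analysis paragraph. N = 40 and about 81% power with 36 evaluable are kept. The other four become secondary. Together with BMI, each lipid measure and symptoms, they are either labelled exploratory or Holm-adjusted as one listed family. Levothyroxine dose, CBC, ESR and the Spearman correlations should be placed explicitly too, for example as exploratory or safety measures.

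**Alternatives that keep several primaries.**
- A fixed sequence: one named antibody at 0.05, and each next outcome only if the one before it is significant. Power for the first test stays about 81%.
- Holm over the two antibodies, with power restated. If both have effect 0.5, power for a named antibody is about 77–79% and for at least one about 83–92% (correlation 0.7 to 0); at correlation 0.9 these are about 76% and 78–79%. If only the named antibody changes, it has about 72%.

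**If outcome data have already been seen,** use Holm across all five and state the lower power for a named antibody: about 60–61% if both antibodies but no hormones change, and about 68–71% if all five have effect 0.5 (correlation 0.7 to 0). The analysis paragraph is partly in the past tense. That alone does not show that data were seen, but the timing should be recorded.

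**Cost.** Wording only, with no extra patients or measurements. Four outcomes lose primary status, or face a later or stricter test.

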 7. CBC
 8. ESR

9. Levothyroxine dose needed to reach euthyroid state

- Intervention:

The Mediterranean diet MD provides close to 30% energy from total fat (19% from MUFA, 5% from PUFA, 9% from SFA), 15% from protein and 55% energy from carbohydrate (Davis et al., 2015).

The daily caloric requirements of each individual will be set according to the age, and physical activity of the patient as per the tables in the Dietary Guidelines of the Americans, published by the United States Department of Agriculture (USDA, 2015-2020).

Reducing dietary goitrogens will be put into consideration when making meal plans.

At first there will be group sessions of 5-7 patients for 2-3 hours where Mediterranean diet and exchange lists will be explained. Then there will be a one to one (doctor to patient) 1 hour session where the 90 days program will be tailored individually to meet the nutritional requirements, food preferences and socioeconomic status of each patient. The patients will be given handouts displaying the caloric content of foods and the different exchange lists.

For the first four weeks of the program, there will be weekly 2 hour sessions. The first hour will be a group meeting where they can gain support from each other and common concerns can be clarified. Then a 1 hour one to one session will be held.

Adherence of participating cases to the diet regimen will be assessed through the recording in their handouts. Any complaint will be recorded and dealt with and any necessary modifications made.

Pre-intervention clinical and laboratory assessment done at 0 months, will be repeated at 3 months

- Study intervention period: 3 months

- Outcome:

measurement of:

1. Anti-TPO

2. Anti-Thyroglobulin
3. TSH, Free T3, Free T4

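### A single-arm before-after comparison cannot show the impact of the Mediterranean diet; the aim and conclusion should be worded as within-patient change

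*Combined protocol and SAP*

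**What the plan says.** Section 2 (Aim/Objectives) states: "This study aims to assess the impact of Mediterranean diet on patients with Hashimoto thyroiditis". It then lists "Primary outcomes: Anti-TPO antibodies, Anti-Thyroglobulin antibodies, TSH, T3, T4" and "Secondary outcomes: BMI, Lipid profile, Symptoms of hypothyroidism".

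Section 3 (Methodology) calls the study a "single-arm open label clinical trial". The first inclusion criterion is "Female and male patients with HT diagnosed by a combination of clinical features of hypothyroidism and presence of anti-thyroid antibodies". It sets no antibody titre, no TSH, T3 or T4 limit, and no date for the qualifying test. Under Sampling Method, every patient with the disease is to be invited.

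On timing, the Intervention text says: "Pre-intervention clinical and laboratory assessment done at 0 months, will be repeated at 3 months". On the diet itself it adds: "Reducing dietary goitrogens will be put into consideration when making meal plans". The last paragraph of Section 1 says that goitrogens inhibit the synthesis of thyroid hormones. The levothyroxine dose required for euthyroidism is in both the baseline list and the outcome list, but nothing says whether it is held constant or allowed for in the analysis.

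Under Statistical Analysis: "The Wilcoxon rank test was used to compare parameters expressed in median and IQR pre- and post-intervention". A P value below 0.05 is called significant. The plan has no control group, run-in or repeated baseline.

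**The concern.** The before-after test asks whether values at 3 months differ from values at 0 months. It does not ask why. With one arm, anything that moves the markers over three months enters the same P value: the Mediterranean pattern, the goitrogen reduction given with it, a change in levothyroxine, the natural course of the disease, or regression to the mean. The aim nevertheless names one cause. If a significant result is read in the words of the aim, the thesis will make a causal claim that its design cannot support.

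The entry criterion raises a narrower worry. Patients must be antibody-positive, and antibodies are primary outcomes and the basis of the sample size. If the value that qualifies a patient is also the month-0 value, the baseline is selected to be high and tends to fall on re-measurement without any treatment effect.

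**Working it through.** **1. The plan's own figure.** Inputs from Sample Size: standardised before-after difference 0.5 in antibody levels, power 80%, alpha 5% (sidedness not stated; two-sided assumed), dropout 10%.

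- Paired t-test: n = 34 (power 0.808); 34/0.9 = 37.8, so 38.
- Signed-rank test, efficiency 3/π: n = 35 (power 0.801); 35/0.9 = 38.9, so 39.

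Both are within 2 of the stated 40, so the size reproduces. Completers: 40 × 0.9 = 36. The sample size is not the problem; the interpretation is.

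**2. What the test can identify.** For each marker,

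observed change = diet + goitrogen reduction + levothyroxine change + natural course + regression to the mean.

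One arm measured twice estimates only the sum. Which rivals apply differs by outcome:

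| Outcome | Goitrogen reduction (Section 1 link) | Levothyroxine change | Natural course | Regression to the mean through entry |
|---|---|---|---|---|
| Anti-TPO, anti-thyroglobulin (primary) | not linked | not excluded | yes | direct, if the sample is shared |
| TSH, T3, T4 (primary) | linked through hormone synthesis | yes | yes | indirect only |
| Symptoms (secondary) | through hormones | yes | yes | direct, if the assessment is shared |

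**3. How large regression to the mean could be.** The documents give neither the selection fraction nor the test-retest correlation, so both are assumptions. Model: log titres are bivariate normal with SD 1 and correlation r; there is no diet effect; a patient qualifies if the qualifying value lies in the upper fraction q of the source population; n = 36; two-sided signed-rank test at 5%.

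If the qualifying value is the baseline, with c the cut-off:

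- mean change = −(1 − r) × φ(c)/q
- variance of change = (1 − r)² × Var(value | qualifies) + (1 − r²)

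For q = 0.5 and r = 0.7, c = 0 and φ(0)/q = 0.399/0.5 = 0.798. The mean change is −0.3 × 0.798 = −0.239. The variance is 0.09 × 0.363 + 0.51 = 0.543, so the SD is 0.737. The standardised change is −0.239/0.737 = −0.32 (simulated: −0.33), against a planning effect of 0.5.

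Simulated chance of a significant fall (nominal 2.5%):

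| Fraction qualifying | r = 0.7 | r = 0.8 | r = 0.9 |
|---|---|---|---|
| 50% | 46% | 32% | 17-18% |
| 70% | 20% | 15% | 9-10% |

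| Fraction qualifying | range over r = 0.7 to 0.9 |
|---|---|
| 80% | 6-12% |
| 90% | 4-6% |
| 95% | 3-4% |
| 98% | about 3% |

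If the baseline is a separate sample not used for eligibility, the larger simulations (8,000 or 20,000 trials per scenario) give 2.2-2.7%, that is, no material inflation.

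**The case against.** A reader might infer that patients are selected on the same quantities as all the primary outcomes, so that regression to the mean alone is likely to give a significant result. The documents do not support that.

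- Entry asks for clinical features of hypothyroidism, not a TSH, T3 or T4 value. Section 1 itself says the disease ranges from euthyroid to overtly hypothyroid, and that most patients need levothyroxine. The direct matches are the antibodies and the secondary outcome of symptoms. For T3 and T4, regression from a hypothyroid state would be a rise, not a fall.
- Entry needs antibodies to be present, not high, and all patients with the disease are invited. If most lie well above the positivity limit, selection is weak and the 90-98% rows apply.
- The text leans towards a separate baseline. Patients are already diagnosed, and a separately headed pre-intervention assessment at 0 months then measures the same markers. The protocol does not rule out a shared sample, but does not describe one either.

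Two further points are fair. The single-arm design is openly declared, and the protocol contains no rule that turns P < 0.05 into a causal statement. The goitrogen link in Section 1 concerns hormones, not the antibodies on which the study was sized.

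These objections stand against a claim built on regression to the mean. They do not answer the attribution problem: the aim is still worded as impact, and no element of the plan separates the diet from its rivals.

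**Conclusion.** The concern holds as a problem of attribution. A significant change in any of the five primary outcomes would not show an effect of the Mediterranean diet, because natural course and co-treatment are uncontrolled and goitrogen reduction is part of the intervention. This follows from the text and needs no assumed figure.

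Regression to the mean is only a possible addition. It acts directly on antibodies and symptoms, and only if the qualifying and month-0 measurements are the same. Under that unstated condition, and with the assumed correlations, the chance of a false significant fall in an antibody runs from barely above nominal to about 46%, depending on how selective entry is. The upper end needs only half of the source population to qualify, for which the documents give no basis, so it should not be quoted as the expected error rate.

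**What to change.** 1. **Restate the aim and the planned conclusion** as within-patient change over 3 months in patients following a goitrogen-reduced Mediterranean diet, without a causal claim. This is the main change.
2. **Report the change in levothyroxine dose** beside the changes in TSH, T3 and T4, so that readers can see whether hormone changes coincide with dose changes. The dose is already collected at both times.
3. **As a clarification**, state that the month-0 sample is the analysis baseline and is not used for eligibility. This mostly writes down what the plan implies.

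Comparing earlier values in the clinic record with month 0 would not be a sound substitute for a control. The earlier qualifying value is itself the selected one, and the interval may differ or include the start of levothyroxine.

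The cost is protocol wording, one added table row and a more modest claim, with no extra visit or patient. Keeping the causal aim would need a concurrent control. As an illustration, if 0.5 were the between-arm standardised difference in change, 2 × (1.960 + 0.842)²/0.25 = 62.8, so 63 per arm; 63/0.9 = 70 per arm, or 140 in total, against the 40 planned.

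### No stable-levothyroxine rule before the 0-month sample, so the pre/post comparison of TSH, T3 and T4 cannot separate a remaining treatment response from a diet effect

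*Combined protocol and SAP*

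**What the plan says.** - **Eligibility** (Section 3, Inclusion Criteria): "Female and male patients with HT diagnosed by a combination of clinical features of hypothyroidism and presence of anti-thyroid antibodies", aged 20 to 50. The exclusions are pregnancy or lactation, age outside that range, and another medical condition. None of these concerns levothyroxine.
- **Recruitment** (Section 3, Sampling Method): a convenience sample in which "all male and female patients with HT will be invited to join the Mediterranean Diet regimen".
- **Expected treatment** (Section 1): "For most HT patients, the hormone-replacement therapy with levothyroxine is indispensable". The same section says that "an anti-inflammatory diet may help HT patients to reduce the need for medicines".
- **Dose data** (Section 3, Pre-intervention Baseline assessment item 9, and Outcome item 6): "Levothyroxine dose needed to reach euthyroid state" is listed at both points. No date of last change is listed.
- **Design and timing** (Section 3, Type of Study and Intervention): a "single-arm open label clinical trial"; "Pre-intervention clinical and laboratory assessment done at 0 months, will be repeated at 3 months".
- **Outcomes** (Section 2): five primary outcomes, namely two antibodies plus TSH, T3 and T4.
- **Analysis** (Section 3, Statistical Analysis): "The Wilcoxon rank test was used to compare parameters expressed in median and IQR pre- and post-intervention". Spearman correlations between study parameters are also planned.

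**The concern.** Levothyroxine acts directly on TSH and T4. If a dose was started or raised shortly before the 0-month sample, part of the hormone response falls inside the 3-month window. With no control arm and no adjustment, the Wilcoxon test counts that response as change under the diet. A recent dose reduction works the other way and could hide a real effect.

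Dose changes during the 3 months are a second route to the same problem. The plan foresees them, since dose is itself an outcome and the Introduction suggests that diet may lower drug needs.

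Three of the five primary outcomes are exposed. The antibody outcomes and the sample size are not in question here. Regression to the mean and spontaneous change are separate limits of a single-arm design and are not part of this point.

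**Working it through.** **1. The plan's own figure.** Inputs from Section 3, Sample Size: effect size 0.5 (assumed there for antibody levels), power 80%, alpha 5% (two-sided assumed), dropout 10%.
- Paired t-test, exact noncentral t: n = 34.
- Wilcoxon signed-rank, relative efficiency 3/π for normal data: 34 × π/3 = 35.6, so 36.
- Dropout: 36 / 0.9 = 40.

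The stated 40 is reproduced. It implies 40 × 0.9 = 36 completers, the number used below.

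**2. Who can enter.** Neither the criteria nor the sampling rule excludes a patient whose dose was started or changed shortly before 0 months.

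**3. Whether the recorded dose would reveal it.** Suppose a dose is changed shortly before 0 months and then held. The dose is the same at 0 and 3 months, so a before/after dose comparison shows nothing, while TSH is still moving. Only the date of the last change identifies this patient.

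**4. Scale for TSH (illustration).** The documents give no figures for this, so the share drifting, its direction, its size and the SD are all assumptions.

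- True diet effect: zero.
- Stable patients: log-TSH change ~ N(0, sd²).
- Drifting patients: N(−ln f, sd²) if TSH falls, N(+ln f, sd²) if it rises, with f = 1.3, 2 or 4.
- Test: z = (W − n(n+1)/4) / √(n(n+1)(2n+1)/24). For n = 36 the mean is 333 and the SD is √4051.5 = 63.65.
- Counted: two-sided P < 0.05 in the direction of a TSH fall (nominal 2.5%), 40,000 runs per cell.

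Chance (%) of a significant TSH fall, for f = 1.3 / 2 / 4:

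| Direction of drift | sd | 4 of 36 | 7 of 36 | 11 of 36 |
|---|---|---|---|---|
| All down | 0.5 | 4.7 / 9.5 / 14.0 | 7.8 / 21.8 / 38.9 | 13.4 / 49.5 / 83.5 |
| All down | 0.8 | 3.8 / 6.6 / 11.3 | 5.2 / 12.9 / 27.9 | 7.7 / 27.1 / 63.2 |
| All down | 1.0 | 3.6 / 5.6 / 9.6 | 4.7 / 10.2 / 22.0 | 6.4 / 19.5 / 50.0 |
| 1-in-4 chance up | 0.5 | 3.4 / 5.2 / 6.9 | 4.6 / 8.5 / 12.4 | 6.2 / 15.0 / 24.1 |
| 1-in-4 chance up | 1.0 | 3.1 / 3.9 / 5.2 | 3.4 / 5.5 / 8.6 | 4.1 / 7.9 / 15.3 |
| Up and down equally likely | all | 2.3–2.6 | 2.3–2.6 | 2.3–2.6 |

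With no drifting patients the rate is 2.5%.

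**5. Sensitivity to the set-up.** Drawing the drifting patients at random, instead of fixing their number, gives all-downward ranges of 3.5–14.7% (10% drifting), 4.9–43.1% (20%) and 6.4–75.0% (30%). A simpler model, with drift of 1 SD of the paired change in one direction, puts the two-sided 5% error rate at about 8%, 18% and 33% for 10%, 20% and 30% drifting (20,000 runs each).

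Only TSH was modelled on the log scale. The same mechanism applies to T3 and T4, but no size is claimed for them.

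**The case against.** The best counter-argument is baseline item 9. Taken literally, the dose that achieves a euthyroid state is known at 0 months only if the patient has already been titrated, so few entrants may be in mid-titration. That reading is reasonable and lowers the likely share. It remains a measurement and not an entry condition, so it keeps nobody out.

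A second argument is that dose is recorded twice, past history is taken and Spearman correlations are planned, so in-study dose changes would be visible. This stands in part: a dose comparison would show such changes. It does not adjust TSH, T3 or T4, and it misses a dose changed just before baseline and then held.

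Third, an uncontrolled pre/post test cannot attribute change to diet under any eligibility rule, so the fix removes one contributor of unknown size. That is true. This contributor differs in that one sentence can largely remove its pre-baseline part without adding an arm.

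Fourth, the high error rates need many patients drifting, all in one direction and by a large amount. That also stands. Balanced drift gives no inflation of the false-positive rate, and the figures are conditional.

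**Conclusion.** The concern holds as a design gap that should be fixed before enrolment. Followed exactly, the plan admits recently started or re-dosed patients and has no means of separating their remaining levothyroxine response from a diet effect on TSH, T3 and T4.

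The actual size cannot be derived from the documents. On the stated assumptions, the false-positive rate for a TSH fall runs from the nominal 2.5% (balanced drift) to about 5–39% with 7 of 36 all drifting downward. Confidence is medium, because the number and direction of such patients are unknown.

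**What to change.** 1. Add an inclusion criterion: *Levothyroxine dose unchanged for at least 8 weeks before the 0-month sample, or untreated for at least 8 weeks with no start planned during the 3 months.* The 8 weeks is a placeholder (consider 6 to 12), for the investigators to confirm before the first enrolment.
2. Defer patients who do not yet meet it and take their 0-month sample when they do. Treatment goes on as usual and is not delayed.
3. Record the date of the last start or change at 0 months, and every change during the 3 months.
4. Keep the primary Wilcoxon comparison in all enrolled patients. As a sensitivity analysis, repeat it for TSH, T3 and T4 in patients whose dose did not change between 0 and 3 months, and report how many changed and in which direction. This subset is selected after baseline, and dose changes may follow TSH or a diet effect, so it supports the main result and does not replace it.

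**Cost.** One sentence, a date field and one repeat of a planned test; the sample size of 40 is untouched. Enrolment will be slower, and patients still being titrated wait longer because each dose step restarts the interval. Results will apply less to newly diagnosed or still-titrating patients. The sensitivity analysis is smaller. For a shift of 0.5 SD (the plan's effect size, set there for antibodies), simulated power is 81.5% with all 36 completers. It is 76.6%, 71.7% or 64.5% if 4, 7 or 11 have a dose change (32, 29 or 25 left).
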